4.3 Follow-up period (EOS)

Follow up visit will be performed at Day 10 for Correction Phase, and 7 \pm 1 days following the last study IP administration in Maintenance Phase, or 7 \pm 1 days following the last study IP administration for patients who are withdrawn from the study medication.

- Subjects will arrive at the clinic in the morning, fasting for at least 8 hours prior to potassium sample collection.
- The clinic staff will solicit any adverse events, note any changes in concomitant medications, and if the subject has visited a doctor or emergency room since the last visit. A final accounting of all ZS dosing supplies will be performed.
- Blood samples for i-STAT potassium and assessment of hematology and clinical chemistry including S-K will be collected.
- Assessment of urinalysis parameters.
- A urine pregnancy test will be performed if the subject is a woman of childbearing potential.

- An ECG will be performed (Section 5.2.3).
- Obtain vital signs (pulse rate and blood pressure) (Section 5.2.4).
- A targeted physical examination including weight (Section 5.2.2).

5. STUDY ASSESSMENTS

The Rave Web Based Data Capture (WBDC) system will be used for data collection and query handling. The investigator will ensure that data are recorded on the electronic Case Report Forms as specified in the Clinical Study Protocol and in accordance with the instructions provided.

The investigator ensures the accuracy, completeness, and timeliness of the data recorded and of the provision of answers to data queries according to the Clinical Study Agreement. The investigator will sign the completed electronic Case Report Forms. A copy of the completed electronic Case Report Forms will be archived at the study site.

5.1 Efficacy assessments

5.1.1 Potassium

Blood samples for determination of potassium will be taken at the times indicated in the Study Plan (see Table 1 and Table 2). Potassium samples will be analyzed locally using i-STAT devices, and serum samples will be prepared and shipped to the Central Laboratory. All serum samples should be examined and any hemolyzed samples MUST be redrawn. In the event that hemolysis or other artefacts are suspected based on the reported i-STAT result the sample may be re-drawn to confirm the result. Only the confirmatory sample result needs to be reported in the eCRF.

5.1.2 Aldosterone and Renin Samples

Aldosterone and renin samples will be collected as summarized in Table 1 and Table 2. Samples will be collected prior to 10 am (1000) after the subject has been upright (sitting or standing) for at least 2 hours and prior to any ECG/physical examination assessments.

Aldosterone samples should be collected into serum separator tubes and renin samples should be collected into EDTA tubes. All samples must be processed to serum (aldosterone) or plasma (renin) according to the central laboratory manual, and immediately frozen (~ -20°C). All serum and plasma samples should be examined and any hemolyzed samples MUST be redrawn.

5.2 Safety assessments

5.2.1 Laboratory safety assessments

Blood and urine samples for determination of clinical chemistry, hematology, and urinalysis will be taken at the times indicated in the Study Plan (see Table 1 and Table 2). Additional

safety samples may be collected if clinically indicated at the discretion of the Investigator. The date, time of collection and results (values, units and reference ranges) will be recorded in the appropriate eCRF module.

The clinical chemistry, hematology and urinalysis will be performed at a central laboratory. Sample tubes and sample sizes may vary depending on laboratory method used and routine practice at the site.

Table 3 Laboratory Safety Variables

Haematology	Clinical Chemistry (serum)
B-Hemoglobin (Hb)	S-Total Protein
B-Hematocrit	S-Albumin
B-Erythrocyte count (RBC)	S-Bicarbonate
B-Total leukocyte count (WBC)	S-Blood Urea Nitrogen
B-Platelet count	S-Creatinine
	S-Bilirubin, total
Urinalysis	S-Alkaline phosphatase (ALP)
U-PH	S-Glucose
U-Specific gravity	S-Sodium
U-Glucose	S-Potassium ¹
U-Ketones	S-Inorganic phosphate
U-Bilirubin	S-Calcium, total
U-Urobilinogen	S-Magnesium
U-Blood	S-Gamma-glutamyl transferase (GGT)
U-Albumin	S-Aspartate aminotransferase (AST)
U-Creatinine	S-Alanine aminotransferase (ALT)
U-Protein	
U-Human chorionic gonadotropin (HCG) (only for females of childbearing potential) ²	Additional Laboratory Tests
	S-Aldosterone
	P-Renin

1. Blood potassium will be tested by i-STAT and Central Laboratory
2. Urine-HCG will be measured at clinic, used the tube provided by Central Laboratory.

The Investigator should make an assessment of the available results with regard to clinically relevant abnormalities. The laboratory results should be signed and dated and retained at

center as source data for laboratory variables. For information on how AEs based on laboratory tests should be recorded and reported, see Section 6.3.

Blood chemistry and hematology parameters will be evaluated fasting, by the Central Laboratory, on Correction Phase Visit 2, 5 and EOS visit for patients NOT entering the Maintenance Phase, and on Maintenance Phase Visits 6 (blood chemistry), 8, 9, 10, 11, 13, 16, 19, 22, 23 and EOS.

The Correction Phase Visit 2 urine pregnancy test for women of childbearing potential is performed as part of the screening procedure prior to any IP administration, Correction Phase EOS visit for patients NOT entering the Maintenance Phase and at Maintenance Phase EOS visit.

Urinalysis, will be performed by the Central Laboratory at Correction Phase Visit 2, 5 and EOS visit for patients NOT entering the Maintenance Phase, and on Maintenance Phase Visits 11, 13, 16, 19, 22, 23 and EOS.

Note: Whenever possible, all blood draws collected prior to meals should be collected prior to insulin/insulin analog treatment.

5.2.2 Physical examination

A complete physical examination should be performed no earlier than 1 day before administration of the first dose of study drug on Correction Phase Visit 2, and targeted physical examination will be conducted during the Correction Phase EOS visit for patients not entering the Maintenance Phase. During the Maintenance Phase targeted physical examinations will be performed at Visits 6, 9, 11, 12, 13, 14, 15, 16, 17, 18, 19, 20, 21, 22, 23 and EOS.

The complete physical examination includes the following: general appearance including skin, height and weight, lymph nodes, thyroid, musculoskeletal/extremities, cardiovascular including assessment of signs of heart failure, lungs, abdomen, and neurological systems.

The targeted physical examination includes the following: weight (weighed on the same scale in the same state of dress), skin, extremities, cardiovascular including assessment of signs of heart failure, lungs, and abdomen.

5.2.3 ECG

5.2.3.1 Resting 12-lead ECG

A 12-lead ECG will be performed after the patient has been lying down for 5 minutes at the times indicated in the Study Plan in Table 1 and Table 2. Heart rate, P and QRS durations, PR and QT intervals will be recorded from standard lead of the computerized quantitative 12-lead ECG.

ECGs will be recorded at Correction Phase Visits 2, 3, 4, 5, EOS visit for patients NOT entering the Maintenance Phase, and on Maintenance Phase Visits 6, 7, 8, 9, 10, 11, 12, 13,

16, 19, 22, 23 and EOS. When applicable ECGs will be performed after the aldosterone and renin samples are drawn and before the first daily dose of IP. In addition, for patients who have i-STAT potassium levels ≥ 6.1 mmol/L or <4.0 mmol/L at the 4 hours post 1st dose time point on the Correction Phase Day 1 (Visit 2), an additional ECG will be recorded 90 minutes post 2nd dose.

5.2.4 Vital signs

5.2.4.1 Pulse rate and blood pressure

Pulse rate and systolic and diastolic blood pressure (BP) will be assessed using non-invasive equipment by an adequately trained health care professional. Measurements with a calibrated sphygmomanometer are preferred. If not available, another device calibrated carefully in proportion to a mercury sphygmomanometer is preferred. Use of aneroid manometers should be avoided. Appropriate cuff size must be used to ensure accurate measurement.

The disappearance of sound (Korotkov phase V) should be used for the diastolic reading. Three (3) readings separated by 2 minutes should be averaged, and the average result will be recorded in the eCRF. If the first two readings of SBP differ by more than 5 mmHg, additional readings should be obtained.

Blood pressure should be checked in both arms at the first visit. Subsequent blood pressure measurements should be recorded in the arm with the higher pressure. Blood pressure should be measured in either supine or sitting position. No shift from one position to another should be made during the study. Supine or sitting posture should be adopted for at least 5 minutes before measurement. The patient should be relaxed and with the arm outstretched and supported. Blood pressure should be measured under standardized conditions, as nearly as possible at the same time each visit, on the same arm, by the same personnel, and with the same apparatus.

5.3 Other assessments

The SF-36 v2 questionnaire will be administered in Japanese. The results will be recorded in the eCRF.

5.4 Pharmacokinetics (Not applicable)

5.5 Pharmacodynamics (Not applicable)

5.6 Genetics (Not applicable)

5.7 Biomarker analysis (Not applicable)

5.8 Storage, re-use and destruction of biological samples

After the analyses are complete the samples will be either completely consumed during the analytical process or disposed of after the analysis.

5.9 Labeling and shipment of biological samples

The Principal Investigator (PI) ensures that samples are labeled and shipped in accordance with the Laboratory Manual and the Biological Substance, Category B Regulations (materials containing or suspected to contain infectious substances that do not meet Category A criteria), see [Appendix B](#).

Any samples identified as Infectious Category A materials are not shipped and no further samples will be taken from the patient unless agreed with AstraZeneca and appropriate labeling, shipment and containment provisions are approved.

5.10 Volume of blood

The total volume of blood that will be drawn from each patient for this study is listed in [Table 4](#) and [Table 5](#) as below. The collection of additional samples is performed locally at the discretion of the investigator and recorded in the eCRF as appropriate, thus requiring additional sample volumes.

Table 4 Volume of blood to be withdrawn from each patient: Correction Phase

Assessment	Sample Volume (mL)	Number of Samples					EOS (D 10)	Maximum blood volume Total (mL)
		V 2 (D 1)	V 3 (D 2)	V 4 (D 3)	V 5 (D 4)			
Hematology	2	1 ²			0-1 ⁴	1	6	
Clinical Chemistry	2.5	1 ²			0-1 ⁴	1	7.5	
Aldosterone and renin	6	1 ²					6	
Potassium (i-STAT and Central Lab S-K)	4.5	3-4 ^{1,5}	2 ³	1	1 ⁵	1 ⁵	40.5	
Maximum blood volume Total (mL)		28.5	9	4.5	9	9	60	

V= Visit; D=Day

- Potassium will be measured twice 60 (±15) minutes apart within 1 day of first dose administration on Correction Phase Day 1(Visit 2) and 4 hours (±15 min) after administration of the first dose of ZS; An extra potassium will be measured at 90 minutes (±15 minutes) after taking the second dose for patients with i-STAT potassium ≥ 6.1 or <4.0 mmol/L at the 4 hour post Dose 1
- On Correction Phase Day 1(Visit 2), the Central Laboratory clinical chemistry, hematology, aldosterone and renin samples will be collected at the same time as the 60 minutes i-STAT screening potassium sample, but will be analysed only in confirmed hyperkalemic subjects.
- Potassium will be measured predose (0 hour) and 1 hour (±15 min) post 1st dose on Correction Phase Day 2 (Visit 3)
- Clinical chemistry and hematology samples only for patients with i-STAT potassium values < 3.5 or ≥ 5.1 mmol/L as measured fasting on Correction Phase Day 4 (Visit 5)

Clinical Study Protocol
Drug Substance ZS
Study Code D9482C00001
Version 5.0
Date 13 Sep 2018

5. Central laboratory S-K sample collected as part of the clinical chemistry

Table 5 Volume of blood to be withdrawn from each patient: Maintenance Phase

Assessment	Sample Volume (mL)	Number of Samples																				Maximum blood volume Total (mL)	
		V6 D1	V7 D2	V8 D5	V9 D12	V10 D19	V11 D26	V12 D54	V13 D82	V14 D110	V15 D138	V16 D166	V17 D194	V18 D222	V19 D250	V20 D278	V21 D306	V22 D334	V23 D362	EOS			
Hematology	2	1	1	1	1	1	1	1	1	1	1	1	1	1	1	1	1	1	1	1	1	1	20
Clinical Chemistry	2.5	1	1	1	1	1	1	1	1	1	1	1	1	1	1	1	1	1	1	1	1	1	27.5
Aldosterone and renin	6																					1	12
Potassium (i-STAT and Central Lab S-K ¹)	4.5	1	1	1	1	1	1	1	1	1	1	1	1	1	1	1	1	1	1	1	1	1	85.5
Maximum blood volume Total (mL)		7	4.5	9	9	9	9	4.5	9	4.5	9	4.5	4.5	15	4.5	4.5	9	4.5	4.5	9	15	9	145

V=Visit; D=Day

- Potassium will be measured fasting prior to the daily dose. Central laboratory S-K sample collected as part of the serum clinical chemistry at Visit 6, 8, 9, 10, 11, 13, 16, 19, 22, 23 and EOS.

6. SAFETY REPORTING AND MEDICAL MANAGEMENT

The Principal Investigator is responsible for ensuring that all staff involved in the study are familiar with the content of this section.

6.1 Definition of adverse events

An adverse event is the development of any untoward medical occurrence in a subject or clinical study subject administered a medicinal product and which does not necessarily have a causal relationship with this treatment. An AE can therefore be any unfavourable and unintended sign (e.g. an abnormal laboratory finding), symptom (for example nausea, chest pain), or disease temporally associated with the use of a medicinal product, whether or not considered related to the medicinal product.

The term AE is used to include both serious and non-serious AEs and can include a deterioration of a pre-existing medical occurrence. An AE may occur at any time, including run-in or washout periods, even if no study treatment has been administered.

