6.2 Definitions of serious adverse event

A serious adverse event is an AE occurring during any study phase, that fulfils one or more of the following criteria:

- Results in death
- Is immediately life-threatening
- Requires in-patient hospitalization or prolongation of existing hospitalization
- Results in persistent or significant disability or incapacity
- Is a congenital abnormality or birth defect
- Is an important medical event that may jeopardize the subject or may require medical intervention to prevent one of the outcomes listed above.

For further guidance on the definition of a SAE, see [Appendix A](#) to the Clinical Study Protocol.

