6.3.6 Adverse events based on examinations and tests

The results from the Clinical Study Protocol mandated laboratory tests and vital signs will be summarised in the Clinical Study Report (CSR). Deterioration as compared to baseline in protocol-mandated laboratory values, vital signs should therefore only be reported as AEs if they fulfil any of the SAE criteria or are the reason for discontinuation of treatment with the investigational product.

If deterioration in a laboratory value/vital sign is associated with clinical signs and symptoms, the sign or symptom will be reported as an AE and the associated laboratory result/vital sign will be considered as additional information. Wherever possible the reporting Investigator uses the clinical, rather than the laboratory term (e.g., anaemia versus low haemoglobin value). In the absence of clinical signs or symptoms, clinically relevant deteriorations in non-mandated parameters should be reported as AE(s).

Any new or aggravated clinically relevant abnormal medical finding at a physical examination as compared with the baseline assessment will be reported as an AE.

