Appendix A Additional Safety Information

Further Guidance on the Definition of a Serious Adverse Event (SAE)

Life threatening

‘Life-threatening’ means that the subject was at immediate risk of death from the AE as it occurred or it is suspected that use or continued use of the product would result in the subject’s death. ‘Life-threatening’ does not mean that had an AE occurred in a more severe form it might have caused death (e.g., hepatitis that resolved without hepatic failure).

Hospitalisation

Outpatient treatment in an emergency room is not in itself a serious AE, although the reasons for it may be (e.g., bronchospasm, laryngeal oedema). Hospital admissions and/or surgical operations planned before or during a study are not considered AEs if the illness or disease existed before the subject was enrolled in the study, provided that it did not deteriorate in an unexpected way during the study.

Important medical event or medical intervention

Medical and scientific judgement should be exercised in deciding whether a case is serious in situations where important medical events may not be immediately life threatening or result in death, hospitalisation, disability or incapacity but may jeopardize the subject or may require medical intervention to prevent one or more outcomes listed in the definition of serious. These should usually be considered as serious.

Simply stopping the suspect drug does not mean that it is an important medical event; medical judgement must be used.

- Angioedema not severe enough to require intubation but requiring iv hydrocortisone treatment
- Hepatotoxicity caused by paracetamol (acetaminophen) overdose requiring treatment with N-acetylcysteine
- Intensive treatment in an emergency room or at home for allergic bronchospasm
- Blood dyscrasias (e.g., neutropenia or anaemia requiring blood transfusion, etc.) or convulsions that do not result in hospitalisation

Development of drug dependency or drug abuse

A Guide to Interpreting the Causality Question

When making an assessment of causality consider the following factors when deciding if there is a ‘reasonable possibility’ that an AE may have been caused by the drug.

- Time Course. Exposure to suspect drug. Has the subject actually received the suspect drug? Did the AE occur in a reasonable temporal relationship to the administration of the suspect drug?

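### Appendix A's exemption for planned admissions reaches those arranged during the study and turns on an undefined idea of unexpected worsening, so some hospitalised deterioration may be missed or classified inconsistently as an SAE

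*Protocol*

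**What the plan says.** Four places in the protocol bear on this.

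- Section 6.1 gives the general definition: "The term AE is used to include both serious and non-serious AEs and can include a deterioration of a pre-existing medical occurrence".
- Section 6.2 lists the criteria that make an adverse event serious. One is "Requires in-patient hospitalization or prolongation of existing hospitalization". The section ends by sending the reader to Appendix A ("For further guidance on the definition of a SAE").
- Appendix A, under Hospitalisation, says: "Hospital admissions and/or surgical operations planned before or during a study are not considered AEs if the illness or disease existed before the subject" entered the study. It then adds a condition: "provided that it did not deteriorate in an unexpected way during the study". The protocol defines neither *unexpected* nor who decides.
- Section 6.3.6 says that worsening of protocol-mandated laboratory values and vital signs "should therefore only be reported as AEs if they fulfil any of the SAE criteria or are the reason for discontinuation of treatment" of the investigational product. It keeps other routes open: signs or symptoms that accompany such worsening are reported, and so is this: "Any new or aggravated clinically relevant abnormal medical finding at a physical examination as compared with the baseline assessment".

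The primary objective (2.1) is 12-month safety and tolerability, with adverse event reporting among its measures. The design is open-label and single-arm (1.4).

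**The concern.** Two features of the Appendix A rule matter. It covers admissions planned during the study, so an admission arranged after ZS has started can qualify. And the exemption is lost only when the worsening was unexpected, so foreseeable worsening leaves it in place.

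The population makes this more than a drafting point. Among patients not on peritoneal dialysis, exclusion criterion 15 removes only those with a documented GFR below 15 mL/min, so advanced kidney disease is eligible. Foreseeable progression with a planned admission is plausible in such patients. Section 1.4 names congestive heart failure and end stage renal failure among the reasons for stopping treatment, so these are outcomes that the trial itself watches.

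The sorting happens at the site, before data entry, and depends on what the investigator expected. With no comparator, expected progression cannot be told apart from a drug effect in an individual patient, and no later analysis can restore an event that was never recorded. About 30 centres are planned, so sites may also apply the rule differently.

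**Working it through.** The protocol gives no SAE rate and no number of planned admissions, so there is no stated figure to reproduce. The check is to apply 6.1, 6.2 and Appendix A to each kind of admission.

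1. **Planned before enrolment, no worsening.** Exempt under Appendix A. Nothing in 6.1 points the other way.
2. **Arranged after enrolment for a pre-existing illness, no worsening.** Exempt. There is no deterioration for 6.1 to capture.
3. **Arranged after enrolment, worsening judged unexpected.** The exemption lapses. The event is an AE, and the admission makes it serious under 6.2.
4. **Unplanned admission, or an illness new since enrolment.** Outside the exemption. Ordinary rules apply.
5. **Arranged after enrolment, worsening judged not unexpected.** The admission is exempt on the literal text. The deterioration falls within what 6.1 allows to be an AE.

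Only case 5 is unsettled, together with its variant in which the admission was planned before enrolment and the illness then worsened as foreseen. A site can defend three classifications:

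- no AE, because the admission is exempt and nothing else is entered;
- a non-serious AE, because the deterioration is entered but the exempt admission is not counted towards seriousness;
- an SAE, because the deterioration is an AE and it led to in-patient admission.

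Section 6.3.6 bears on a small part of case 5. Suppose the worsening is purely a mandated laboratory value, with no symptom, no examination finding and no discontinuation of ZS, and hospitalisation is the only seriousness criterion in play. Whether the admission counts then decides whether anything is recorded as an AE.

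**Direction.** Compared with counting every case 5 event as serious, the first two classifications remove an SAE and none adds one. If S patients out of N would have an SAE under that full count, and k of them have no SAE other than an exempted admission, the reported proportion is (S − k)/N instead of S/N. The shortfall is k/N, which is zero or positive.

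**Size.** Neither S nor k can be obtained from the protocol. N for the primary objective is the Maintenance Phase safety set, which will be smaller than the 150 entering the Correction Phase if any of them fail to reach normokalaemia. The shortfall cannot be quantified.

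**Timing.** Section 3.3 treats a patient as enrolled once the consent form is signed, and 6.3.1 starts AE collection at consent. Consent is therefore a natural cut-off for a narrower exemption.

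**The case against.** The strongest reply is that the passages fit together. Section 6.1 is permissive: it says what an AE can include. Section 6.2 applies only to events that are already AEs, and it invokes Appendix A as guidance. A reader might infer a flat contradiction between 6.1 and Appendix A; the documents do not support that. This part of the reply stands.

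The exemption also concerns the admission or operation. Appendix A does not say that the worsening behind it stops being an AE, and that worsening can be serious under another 6.2 criterion, such as an important medical event. This stands too, and it limits the point.

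A reader might further infer that 6.3.6 shuts the remaining way in, so that such cases vanish altogether. It does not. Symptoms accompanying a laboratory change are reportable, as are aggravated examination findings, and targeted examinations covering weight, extremities, lungs and signs of heart failure recur through the Maintenance Phase (5.2.2). Laboratory worsening that leads to discontinuation is reportable, and 1.4 says stopping rules apply to congestive heart failure and end stage renal failure. Section 6.3.5 collects whatever the patient reports or staff observe. Section 8.5.2 analyses oedema-related events by named term and follows creatinine, eGFR, UPCR and UACR over time, so a renal signal would not be lost.

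These routes secure the recording of most deteriorations. They do not settle whether a case 5 event is serious, and Appendix A, the place a site would look, points away from counting it. That matters for the SAE count and for the narratives that 8.5.2 requires for serious events.

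**Conclusion.** The point holds in a limited form. Appendix A leaves room for an admission arranged after enrolment, for foreseeable worsening of a pre-existing disease, to be left out of the SAE count or classified differently between sites, depending on investigator judgement. The possible bias is downward, confined to planned admissions for worsening judged not unexpected, and of unknown size.

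A reader might conclude that planned admissions for kidney or heart-failure progression drop out as a class, or that the SAE rate is understated by a particular amount. Neither is supported. The protocol nowhere classes such progression as expected, and any percentage would rest wholly on assumed rates, on every such admission being exempted, and on those patients having no other SAE.

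The conclusion rests on reading Appendix A literally and on sites following it. It merits correction because it is a stated rule that filters primary-outcome data before entry, and because it is cheap to put right.

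**What to change.** In Appendix A, limit the exemption to admissions or operations planned before informed consent for a condition that has not worsened since consent. Add that worsening of a pre-existing disease leading to an admission or operation arranged after consent is recorded as an AE and judged for seriousness under 6.2, whether or not it was expected. Refer to this sentence from 6.1 and 6.2.

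This changes event recording only and leaves clinical management as it is. The cost is one wording edit with cross-references, a few more SAE forms and narratives, and possibly a slightly less favourable reported SAE rate.
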